1. PROTOCOL SYNOPSIS

Name of Sponsor/Company: Acceleron Pharma Inc. [name]
Name of Investigational Product: Luspatercept (ACE-536)
Name of Active Ingredient: ACE-536
Title of Study: An Open-Label Extension Study to Evaluate the Long-Term Effects of ACE-536 in Patients with β-Thalassemia Previously Enrolled in Study A536-04
Study Centers: up to 15
Phase of Development: 2
Objectives: Primary: 
To evaluate the long-term safety and tolerability of ACE-536 in patients with β-thalassemia who were previously enrolled in study A536-04. Secondary: 
To evaluate erythroid response defined as the proportion of patients with:
Mean hemoglobin increase ≥ 1.5 g/dL over a continuous 12-week interval compared to baseline in non-transfusion dependent (NTD) patients, not influenced by red blood cell (RBC) transfusion, ORReduction in RBC transfusion burden by $\geq 50\%$ over a continuous 12-week interval compared to the 12 weeks prior to the start of treatment in transfusion dependent (TD) patients.To evaluate erythroid response defined as proportion of patients with:
Mean hemoglobin increase ≥ 1.5 g/dL over a continuous 8-week interval compared to baseline in NTD patients, not influenced by RBC transfusion, ORReduction in RBC transfusion burden by $\geq 20\%$ over a continuous 8-week interval compared to the 8 weeks prior to the start of treatment in TD patients.To evaluate the time to erythroid response and duration of erythroid response.To evaluate the mean change from baseline over an 8- or 12-week period in hemoglobin level in NTD patients not influenced by RBC transfusionTo evaluate the mean % change from baseline in transfusion burden over an 8- or 12-week period in TD patients.To evaluate the mean change in pre-transfusion hemoglobin levels in TD patientsTo evaluate changes in markers of erythropoiesis, hemolysis, iron overload, and iron metabolism

- To examine the pharmacokinetic (PK) profile of ACE-536 in patients with β -thalassemia

Exploratory:

- To evaluate biomarkers related to the transforming growth factor beta (TGF- β) superfamily
- To evaluate patient self-reported quality of life using tools including but not limited to the Functional Assessment of Cancer Therapy-Anemia Scale (FACT-An) and Short Form (36) Health Survey (SF-36) questionnaires
- To evaluate change in extramedullary hematopoiesis (EMH) mass size by MRI
- To evaluate change in spleen size by MRI
- To evaluate change in bone mineral density (BMD) by DXA
- To evaluate change in leg ulcers
- To evaluate change in the 6-minute walk test (6MWT) distance in NTD patients

Methodology

Study Design:

This open-label extension study will evaluate the effects of up to 60 months of ACE-536 treatment in patients with β -thalassemia previously enrolled and treated with ACE-536 for up to 3 months in study A536-04. The base study (A536-04) is a phase 2, open-label, ascending dose study to evaluate the effects of ACE-536 in patients with β -thalassemia. A total of up to 64 patients may be enrolled in study A536-04 and may be eligible for study A536-06.

Consenting patients that meet the A536-06 eligibility criteria may immediately roll over from A536-04 to study A536-06 following the last ACE-536 dose. These patients may forego the End of Study (EOS) visit in study A536-04 to begin study A536-06. For these patients, Cycle 1 Day 1 (C1D1) of study A536-06 may take place 28 (\pm 7) days after the last dose administered in study A536-04, which may coincide with the patient's A536-04 End of Treatment (EOT) visit. These patients are considered "patients without treatment interruption".

Patients who complete the EOS visit for study A536-04 and are \geq 28 days post EOS visit are considered "patients with treatment interruption" and will be re-assessed for eligibility by meeting all eligibility criteria plus additional inclusion criteria, as defined in [Section 9.3](#).

Patients who do not meet the above criteria (e.g., $>$ 35 days after last dose in study A536-04 and $<$ 28 days post EOS visit in study A536-04) may still participate, but should be treated as patients with treatment interruption and should not begin study A536-06 C1D1 until they have reached \geq 28 days post EOS visit from study A536-04 so that new baseline assessments can be measured.

For patients without treatment interruption, transfusion status (NTD or TD) will carry-over from the base study A536-04. For NTD patients with treatment interruption, transfusion status will be reassessed prior to C1D1 of study A536-06. NTD patients with treatment interruption are defined as patients who require transfusion of $<$ 4 units of RBCs over the 8 weeks prior to Cycle 1 Day 1 of study A536-06. For TD patients with treatment interruption, transfusion status will carry-over from the base study A536-04.

A patient without treatment interruption may continue to be dosed with ACE-536 at the same dose level (rounded to nearest A536-06 starting dose level) administered at their last dose in

study A536-04 (unless a dose reduction is required based upon patient dose modification rules from study A536-06). All patients with treatment interruption will be initially treated with ACE-536 at a starting dose level of 0.8 mg/kg which has been determined to be safe and well tolerated by the Safety Review Team (SRT) based on data from study A536-04.

Each TD patient will have a defined “pre-transfusion hemoglobin threshold” which will be calculated based on transfusion history and will be used for determining when to transfuse during the study. The baseline pre-transfusion hemoglobin threshold will be the mean of all documented pre-transfusion hemoglobin values during the 12 weeks prior to C1D1 of base study A536-04 (for patients without treatment interruption) or study A536-06 (for patients with treatment interruption). During treatment, if the pre-transfusion hemoglobin level is increased by ≥ 1 g/dL compared to the baseline pre-transfusion hemoglobin threshold for that patient, transfusion should be delayed by a minimum of 7 days and/or the number of units transfused should be reduced by 1 or more RBC units. Patients may be transfused at the investigator’s discretion for symptoms related to anemia or other requirements (e.g., infection).

Patients will participate in the extension study A536-06 for up to 97 months, including a 28-day (1 month) screening period, a 60-month treatment period and a 3-year (36 months) follow-up period.

The SRT established for study A536-04 will review safety data and pharmacodynamic (PD) data periodically throughout study A536-06.

Starting Dose Levels

A patient without treatment interruption may continue to be dosed with ACE-536 at the same dose level (rounded to nearest A536-06 starting dose level) administered at their last dose in study A536-04 (unless a dose reduction is required based upon patient dose modification rules from study A536-06). All patients with treatment interruption will be initially treated with ACE-536 at a starting dose level of 0.8 mg/kg which has been determined to be safe and well tolerated by the Safety Review Team (SRT) based on data from study A536-04. Examples of possible starting dose levels with dose modifications (reductions and titrations) are below for reference.

Examples of Possible Starting Dose with Dose Modifications (Reductions and Titrations)

3 rd Dose Reduction	2 nd Dose Reduction	1 st Dose Reduction	Starting Dose Level	1 st Dose Titration	2 nd Dose Titration
0.2 mg/kg	0.4 mg/kg	0.6 mg/kg	0.8 mg/kg	1.0 mg/kg	1.25 mg/kg
0.4 mg/kg	0.6 mg/kg	0.8 mg/kg	1.0 mg/kg	1.25 mg/kg	
0.6 mg/kg	0.8 mg/kg	1.0 mg/kg	1.25 mg/kg		

- Starting dose level for TD and NTD patients to be determined based on data from study A536-04 (range: 0.2-1.25 mg/kg).
- Starting dose level for patients without treatment interruption will be last dose level (rounded to nearest A536-06 starting dose level) administered in study A536-04 unless a dose reduction is required based upon patient dose modification rules from study A536-06.
- Patients may be titrated up and down dose levels as required per protocol to meet dose modification and titration rules.
- Patients who require more than 2 dose reductions due to an AE should be discontinued from treatment and complete the EOT and EOS visits.
- The maximum dose titration will not exceed the maximum dose level tested in base study A536-04.

Individual Dose Modification Rules

The following dose modification rules include both PD and safety parameters which may require a dose delay and/or a dose reduction. These rules should be assessed prior to every dosing visit for all patients. If a dose delay is required, the patient should have weekly visits to assess hematology results and adverse events (AE) until the patient is eligible to receive the next dose of ACE-536.

Observation on Dosing Day	Action	ACE-536 Dose Modification
Hemoglobin \geq 13 g/dL	Hold dose and monitor patient weekly until hemoglobin $<$ 12 g/dL	Resume dosing once hemoglobin $<$ 12 g/dL at the same dose level
Hemoglobin increase \geq 2 g/dL from the previous dosing day (not attributable to RBC transfusion)	Continue dosing	Reduce the dose by 1 dose level
Non-hematologic AE \geq Grade 3, or hematologic AE \geq Grade 4, at least possibly related to study drug	Hold dose and monitor patient weekly until resolution of AE to \leq Grade 1 or baseline	Resume dosing upon resolution of the AE to \leq Grade 1 or baseline and reduce the dose by 1 dose level ^a
Grade 3 leukocytosis (WBC $>100,000/\mu\text{L}$)		Discontinue treatment

^a Patients who require more than 2 dose reductions due to an AE should be discontinued from treatment and complete the EOT, PTFU, LTFU, and EOS visits.

Individual Dose Titration for NTD Patients

For all NTD patients (with and without treatment interruption), the dose level will be assessed for titration at Day 1 of every cycle starting at C3D1 (e.g., C3D1, C4D1, C5D1, etc.). The dose level should be titrated individually for each patient not to exceed the maximum dose level evaluated in the base study A536-04 as follows:

- If hemoglobin increase from baseline is $<$ 1.5 g/dL throughout the previous two cycles at the same dose level, the dose level will be increased by 1 dose level (unless dose modification is required).
- If hemoglobin increase from baseline is \geq 1.5 g/dL but not sustained for at least two consecutive measurements during the previous two cycles at the same dose level, the dose level will be increased by 1 dose level (unless dose modification is required).
- If hemoglobin increase from baseline is \geq 1.5 g/dL for at least two consecutive measurements during the previous two cycles at the same dose level, the dose level will be unchanged (unless dose modification is required).

Baseline hemoglobin to assess titration will be the average of two or more measurements performed during the screening period for base study A536-04 (for patients without treatment interruption) or study A536-06 (for patients with treatment interruption). Hemoglobin measurements within 2 weeks following RBC transfusion will be excluded from both the calculation of the mean baseline hemoglobin and for evaluation of dose titration for a patient during treatment.

Individual Dose Titration for TD Patients

For all TD patients (with and without treatment interruption), the dose level will be assessed for titration at Day 1 of every cycle starting at C3D1 (e.g., C3D1, C4D1, C5D1, etc.). The dose

level should be titrated individually for each patient not to exceed the maximum dose level evaluated in the base study A536-04 as follows:

- If patient is transfused with ≥ 3 units during the previous 2 cycles at the same dose level, the dose level will be increased by 1 dose level (unless a dose modification is required).

Number of patients: A planned total of up to 64 patients who enrolled in base study A536-04 may be eligible for the extension study A536-06.

Inclusion Criteria:

All patients must meet the following criteria

1. Completion of the treatment period in the base study A536-04.
2. Females of child bearing potential (defined as sexually mature women who have not undergone hysterectomy or bilateral oophorectomy, or are not naturally postmenopausal ≥ 24 consecutive months) must have negative urine or blood pregnancy test prior to enrollment and use adequate birth control methods (abstinence, oral contraceptives, barrier method with spermicide, or surgical sterilization) during study participation and for 12 weeks following the last dose of ACE-536. Males must agree to use a latex condom during any sexual contact with females of child-bearing potential during study participation and for 12 weeks following the last dose of ACE-536, even if he has undergone a successful vasectomy. Patients must be counseled concerning measures to be used to prevent pregnancy and potential toxicities prior to the first dose of ACE-536.
3. Patient is able to adhere to the study visit schedule, understand and comply with all protocol requirements.
4. Patient understands and is able to provide written informed consent.

Patients with treatment interruption (defined as patients who complete the EOS visit for study A536-04 and are ≥ 28 days post EOS visit) must also meet the following criteria

5. Mean hemoglobin concentration < 10.0 g/dL of 2 measurements (not influenced by RBC transfusion) (one performed within one day prior to Cycle 1 Day 1 and the other performed during the screening period [Day -28 to Day -1]) in NTD patients.
6. Adequate folate levels or on folate therapy.
7. Platelet count $\geq 100 \times 10^9/L$ and $\leq 1,000 \times 10^9/L$.
8. Aspartate aminotransferase (AST) or alanine aminotransferase (ALT) $< 3 \times$ upper limit of normal (ULN).
9. Serum creatinine $\leq 1.5 \times$ ULN.
10. Ejection fraction $\geq 50\%$ by Echocardiogram (ECHO) or Multi gated acquisition scan (MUGA).

Exclusion Criteria:

All patients must not meet any of the following criteria

1. Discontinuation/withdrawal from study A536-04 due to patient request, patient unwillingness or inability to comply with the protocol, pregnancy, use of prohibited

medication (e.g., hydroxyurea), medical reason or AE, hypersensitivity reaction to the study drug, at the discretion of the sponsor, or loss to follow-up prior to completion of the treatment period.

2. Any clinically significant pulmonary (including pulmonary hypertension), cardiovascular, endocrine, neurologic, hepatic, gastrointestinal, infectious, immunological (including clinically significant allo- or auto-immunization) or genitourinary disease considered by the investigator as not adequately controlled prior to Cycle 1 Day 1.
3. Symptomatic splenomegaly.
4. Splenectomy within 56 days prior to Cycle 1 Day 1.
5. Major surgery (except splenectomy) within 28 days prior to Cycle 1 Day 1. Patients must have completely recovered from any previous surgery prior to Cycle 1 Day 1.
6. Patients receiving or planning to receive hydroxyurea treatment. Patients must not have had hydroxyurea within 90 days of Cycle 1 Day 1.
7. For patients with treatment interruption: Iron chelation therapy if initiated within 56 days prior to Cycle 1 Day 1.
8. Cytotoxic agents, systemic corticosteroids, immunosuppressants, or anticoagulant therapy such as warfarin or heparin within 28 days prior to Cycle 1 Day 1 (prophylactic aspirin up to 100 mg/day and low molecular weight (LMW) heparin for superficial vein thrombosis (SVT) is permitted).
9. Treatment with another investigational drug (including sotatercept [ACE-011]) or device, or approved therapy for investigational use \leq 28 days prior to Cycle 1 Day 1, or if the half-life of the previous investigational product is known, within 5 times the half-life prior to Cycle 1 Day 1, whichever is longer at any time between the end of treatment of the base study A536-04 and Cycle 1 Day 1.
10. Known positive for human immunodeficiency virus (HIV), active infectious hepatitis B (HBV) or active infectious hepatitis C (HCV).
11. Uncontrolled hypertension defined as systolic blood pressure (SBP) \geq 150 mm Hg or diastolic blood pressure (DBP) \geq 100 mm Hg.
12. Known history of thromboembolic events \geq grade 3 according to the National Cancer Institute-Common Terminology Criteria for Adverse Events (NCI-CTCAE) v.4.0 (current active minor version).
13. Pregnant or lactating females.
14. History of severe allergic or anaphylactic reactions or hypersensitivity to recombinant proteins or excipients in the investigational drug.
15. Any other condition not specifically noted above which, in the judgment of the investigator, would preclude the patient from participating in the study.

Investigational product, dosage and mode of administration:

ACE-536 drug product will be provided as either a sterile liquid formulation or a lyophilized powder formulation for reconstitution with water. Each single-use vial of the liquid formulation contains 25 mg of ACE-536 in a 0.5 mL Tris-buffered saline solution (50 mg/mL). Each single-use vial of the lyophilic formulation may contain either 25 mg, 50 mg, or 75 mg ACE-536 for reconstitution with 0.5 mL, 1 mL, or 1.5 mL water, respectively, to form a citrate-buffered solution (50 mg/mL) for injection.

ACE-536 will be administered by SC injection on Day 1 of each cycle.

Criteria for Evaluation

Safety Assessments:

- All patients will be assessed for safety by monitoring AEs, clinical laboratory tests, vital signs, electrocardiogram (ECG), anti-drug antibody (ADA) testing, abdominal MRI/ultrasound and physical examination.

Efficacy Assessments:

- Patients will be assessed for erythroid response over a 62-month period following initiation of treatment. Erythroid response endpoints will be determined by monitoring hematologic laboratory values and RBC transfusions.
- Other secondary efficacy endpoints will be assessed by examining other hematology, erythropoiesis, hemolysis, iron overload, and iron metabolism parameters.
 - Erythropoiesis parameters may include serum erythropoietin (EPO) levels, reticulocytes, nucleated RBCs and soluble transferrin receptor
 - Iron overload/metabolism parameters may include serum iron, total iron binding capacity (TIBC), transferrin, soluble transferrin receptor, calculated transferrin saturation, ferritin, non-transferrin bound iron (NTBI), hepcidin, Liver iron content (LIC), and iron chelation therapy use.

PK Assessments:

- Blood samples will be drawn to evaluate PK parameters.

Exploratory Assessments:

- Biomarkers related to the TGF- β superfamily
- Self-reported quality of life measures including but not limited to the FACT-An and SF-36 questionnaires
- Extramedullary hematopoiesis (EMH) mass size by MRI
- Spleen size by MRI
- Bone mineral density (BMD) by DXA
- Leg ulcer size
- 6-minute walk test (6MWT) distance in NTD patients.

Statistical Methods

Sample Size Calculation:

There is no formal sample size calculation for the study although up to 64 patients may participate from the A536-04 study.

Analysis Populations:

The modified Intent-to-Treat (mITT) Population: All patients enrolled in the study who received at least one dose of ACE-536.

Efficacy Evaluable (EE) Population: All patients administered at least one dose of ACE-536 and have 1) at least three hemoglobin assessments over an 8-week period, not influenced by transfusion, in NTD patients, OR, 2) at least 8 consecutive weeks of transfusion frequency data in TD patients.

Pharmacokinetics Population: All patients who received at least 1 dose of ACE-536 during Study A536-06 and have sufficient serum ACE-536 values for PK analysis.

Primary Endpoint Analysis:

Safety analysis: To assess clinical safety, all AEs, vital sign measurements and clinical laboratory information will be summarized. AEs will be coded using the Medical Dictionary for Regulatory Activities (MedDRA). Changes from baseline for clinical laboratory values and vital signs will be summarized over time. Descriptive statistics and shift tables will be generated as appropriate. Disposition rates will be summarized.

Efficacy/Pharmacodynamic Effects Analysis of Secondary Endpoints:

All efficacy analyses will be performed for the EE and mITT populations.

Efficacy will be evaluated by determining the proportion of β -thalassemia patients who have an erythroid response, defined as 1) a mean hemoglobin increase ≥ 1.0 g/dL or ≥ 1.5 g/dL over an 8-week or 12-week period as compared to baseline, not influenced by RBC transfusion in NTD patients or 2) $\geq 20\%$ or $\geq 50\%$ reduction in RBC transfusion burden over an 8-week or 12-week period as compared to the 8-week or 12-week period pretreatment in TD patients.

Baseline hemoglobin for NTD patients will be the average of two or more measurements performed during the screening period for base study A536-04 (for patients without treatment interruption) or study A536-06 (for patients with treatment interruption). Hemoglobin measurements within 2 weeks following RBC transfusion will be excluded.

Transfusion burden for TD patients will be defined as the ratio of RBC transfusion units (or mLs) transfused during an interval divided by the duration of that interval, where the interval may be during the pretreatment period or the treatment plus follow-up period. The interval during the pretreatment period will be defined as the 8 or 12 weeks prior to Cycle 1 Day 1 of base study A536-04 (will also be analyzed using pretreatment period of study A536-06 for patients with treatment interruption). An interval during the treatment plus

follow-up period will be defined as an 8-week or 12-week interval after Cycle 1 Day 1 of study A536-06.

The erythroid response, as defined above, will also be evaluated using other pre-treatment and on-treatment intervals and other % reductions in RBC units transfused, including 100% (transfusion-free).

The erythroid response will be summarized using both a point estimate and its exact 95% confidence interval (CI) based on binomial distribution.

No direct comparison testing with concurrent or historical controls will be performed.

Analysis of other secondary efficacy/PD endpoints will include:

- Time to erythroid response and duration of erythroid response
- Change/percent change from pretreatment in mean transfusion burden in TD patients
- Change in mean hemoglobin level in NTD patients
- Change in pre-transfusion hemoglobin levels in TD patients (including analysis of patient subset with < 20% change in transfusion burden)
- Change from baseline in erythropoiesis parameters, including EPO, reticulocytes, nucleated RBCs, and soluble transferrin receptor
- Change from baseline in hemolysis parameters, including total/indirect bilirubin, and lactate dehydrogenase (LDH)
- Change from baseline in iron overload and iron metabolism parameters, including serum iron, TIBC, transferrin, calculated transferrin saturation, soluble transferrin receptor, ferritin, NTBI, hepcidin, iron chelation therapy use and LIC by MRI.

The exploratory endpoints will include evaluation of biomarkers related to the TGF- β superfamily, quality of life, change in EMH mass size, change in spleen size (in patient subset with no prior splenectomy), change in BMD, change in leg ulcer size, and change in the 6MWT distance in NTD patients .

All binary endpoints will be summarized using both a point estimate and its exact CI based on the binomial distribution. The time-to-event type secondary endpoints will be analyzed using Kaplan-Meier method to estimate the survival curve and median time to event and 95% CI.

Anti-drug antibody analysis: The results of anti-drug and neutralizing antibody testing for ACE-536 and human ActRIIB protein versus time will be presented. Exploratory analysis will be performed on the potential effect of ADA on ACE-536 PK and drug exposure if ADA tests are deemed positive.

Pharmacokinetics analysis: PK parameters for ACE-536, such as maximum serum concentration (C_{max}), time to maximum concentration (t_{max}), and area under the concentration/time curve (AUC), will be estimated using non-compartmental and/or single compartment analysis, as appropriate. Dose proportionality may be assessed using the exposure data (e.g., C_{max} , AUC) if sufficient dose levels are studied. Descriptive statistics will

be provided for serum concentrations and PK parameters. The relationship between ACE-536 exposure and response (i.e., safety, efficacy, and biomarkers) may be explored, as appropriate.

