9.3. Selection of Study Population

9.3.1. Transfusion Status

- For patients without treatment interruption patient transfusion status (NTD or TD) will carry-over from the base study A536-04.
- For NTD patients with treatment interruption, patient transfusion status will be reassessed prior to C1D1 of study A536-06.
 - NTD patients with treatment interruption are defined as patients who require transfusion of < 4 units of RBCs over the 8 weeks prior to Cycle 1 Day 1 of study A536-06.
- For TD patients with treatment interruption, patient transfusion status will carry-over from the base study A536-04.

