5. STATISTICAL METHODOLOGY

5.1. Definitions

Transfusion Status

For patients without treatment interruption, transfusion status (NTD or TD) will carry-over from the base study A536-04.

For NTD patients with treatment interruption, transfusion status will be reassessed prior to C1D1 of study A536-06. NTD patients with treatment interruption are defined as patients who require transfusion of < 4 units of RBCs over the 8 weeks prior to Cycle 1 Day 1 of study A536-06.

For TD patients with treatment interruption, transfusion status will carry-over from the base study A536-04.

Transfusion Dependent (TD) Defined in Base Study A536-04

Based on the protocol, TD patients are defined as those who required ≥ 4 units of RBCs every 8 weeks (confirmed over 6 months prior to study A536-04 Cycle 1 Day 1). For statistical programming purposes, a patient is defined as TD if the total RBCs is ≥ 11 units during 26 weeks on or prior to study A536-04 Cycle 1 Day 1.

Non-transfusion Dependent (NTD) Defined in Base Study A536-04

NTD patients are those who do not meet the above definition for TD. For statistical programming purposes, NTD patients are defined as those who received < 11 units of RBCs during 26 weeks on or prior to study A536-04 Cycle 1 Day 1.

Baseline

For patients who roll over to Study A536-06 without interruption, the baseline for Study A536-04 will be used as the baseline for Study A536-06 for all measurements, as further defined below. For patients who enter Study A536-06 with interruption, the baseline for Study A536-06 will be used, as further defined below. For assessments that are not scheduled to be done or with an inadequate data collection window at the beginning of Study A536-06, the baseline for Study A536-04 will be used as the baseline for Study A536-06.

Baseline Hemoglobin

Baseline hemoglobin will be the average of hemoglobin measurements within 28 days of Cycle 1 Day 1, excluding measurements within 14 days following RBC transfusion.

Baseline Transfusion Burden

Baseline transfusion burden will be calculated as the total amount of RBC transfusions during the 12 weeks on or prior to Cycle 1 day 1.

Baseline for Other Parameters

Baseline erythropoietin (EPO) is defined as the maximum test value within 28 days prior to Cycle 1 Day 1. For all other parameters, baseline is defined as the last observation on or prior to Cycle 1 Day 1.

Transfusion Unit Conversion

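### Interrupted NTD patients are re-classified on an 8-week window that lies inside their SAP baseline-burden window, which biases the fixed-window TD response rates upward for any patient moved to TD

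*Protocol*

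**What the plan says.** **Who is reassessed.** The Protocol Synopsis, Protocol 9.1 and 9.3.1, and SAP 3.1 and 5.1 give the same rule. Patients without interruption keep their A536-04 status. For the interrupted, "For NTD patients with treatment interruption, transfusion status will be reassessed prior to C1D1 of study A536-06", whereas "For TD patients with treatment interruption, transfusion status will carry-over from the base study A536-04".

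**On what window.** Interrupted NTD patients are those who "require transfusion of < 4 units of RBCs over the 8 weeks prior to Cycle 1 Day 1 of study A536-06". The documents do not name the status of a patient with 4 or more units. TD is the only other category they use.

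**How base-study status was set.** SAP 5.1 gives the A536-04 programming rule: "a patient is defined as TD if the total RBCs is ≥ 11 units during 26 weeks". Below that total the patient is NTD.

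**Baseline burden.** SAP 5.1 uses the A536-06 baseline for interrupted patients and defines burden as the "total amount of RBC transfusions during the 12 weeks on or prior to Cycle 1 day 1". If the A536-06 data window is inadequate, the A536-04 baseline is used. The Protocol Synopsis and 15.2.3 take the 8 or 12 weeks before A536-04 C1D1 as the pretreatment interval, and add the A536-06 pretreatment period as a further analysis for interrupted patients. SAP 5.12.6 lists two changes (baseline hemoglobin and removal of the EE population). The burden window is not among them.

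**Endpoints.** SAP 5.7.2.1 reports TD reductions of at least 33% and 50% in weeks 13-24 and 37-48, and reductions over rolling 8-, 12- and 24-week intervals. All summaries are descriptive.

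**The concern.** Suppose a patient of modest long-run use returns after an interruption and happens to have had 4 units in the last 8 weeks. Base-study status would have needed 11 units in 26 weeks, so this patient could have as few as 4 of the 11 and still lose NTD status. If the patient is then analysed as TD, the SAP baseline contains the very weeks that triggered the move. That baseline is high by selection, and later use tends to fall back toward the patient's usual level without any drug effect. The fall counts as a TD response.

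Nothing offsets this in the other direction, because an interrupted TD patient with a quiet 8 weeks is not moved to NTD. The study has no control arm and plans no comparison testing. Neither document plans a separate display or a sensitivity analysis for re-classified patients.

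**Working it through.** The plan gives no figure to reproduce. The question is how much response the selection produces when the drug does nothing.

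**Inputs from the documents.** The move is triggered at 4 or more units in 8 weeks. The base-study cut is 11 units in 26 weeks. Baseline is the last 12 weeks. Response is scored in weeks 13-24.

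**Assumptions (not in the documents).** Use is constant, with Poisson episodes of 2 units each, at a long-run R = 4, 6 or 8 units per 26 weeks, and there is no drug effect.

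**Step 1: chance of the trigger.** Mean episodes in 8 weeks: m = (R/2) × 8/26 = 0.615, 0.923, 1.231. Four units means two or more episodes, so P = 1 − e^(−m)(1 + m) = 12.7%, 23.6%, 34.8%. Requiring also fewer than 11 units in the same 26 weeks leaves about 12%, 18% and 20% (simulation). These are the patients who meet only the 8-week rule.

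**Step 2: what the selection does to baseline.** The true 12-week mean is R × 12/26. Simulated means in the selected patients are higher:

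| R per 26 weeks | True 12-week mean | Mean baseline if selected |
|---|---|---|
| 4 | 1.8 | 4.9 |
| 6 | 2.8 | 5.2 |
| 8 | 3.7 | 5.3 |

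**Step 3: reduction of at least 50% in weeks 13-24, no drug effect.** The comparator is all patients with a nonzero baseline. Giving the selected patients a separate 12-week baseline that does not overlap the trigger yields the same comparator figures to within 0.2 points, so the difference is the selection effect.

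| R | Selected, overlapping baseline | Comparator | Excess |
|---|---|---|---|
| 4 | 77.5% | 54.4% | 23.1 |
| 6 | 62.3% | 45.4% | 16.9 |
| 8 | 48.5% | 38.8% | 9.7 |

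Separate runs agree to within about one point. At constant use, weeks 37-48 behave the same way.

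**Step 4: other assumptions.** With 1- or 2-unit episodes, 0.5 to 3 units per 8 weeks, and no 11-unit limit, the excess ranges from 12 to 43 points. The direction is stable; the size depends on the assumed rate.

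**Step 5: rolling windows.** For a reduction of at least 50% in any 12-week interval within 48 weeks, selected patients reach about 99-100% and all patients with a nonzero baseline about 92-98%. Selection adds only about 2 to 7 points; the search over many intervals produces the rest.

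**Step 6: effect on a reported rate.** If the TD set had 30 patients (assumed), one re-classified patient could move a rate by at most 1/30 = 3.3 points. The expected part due to selection is 0.10 to 0.23 × 3.3 = 0.3 to 0.8 points.

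**The case against.** **The move to TD is not written.** This is correct. The text says only who is NTD, and the SAP's TD definition is tied to A536-04 C1D1. What stands is that the status at 4 or more units is undefined and TD is the natural reading.

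**The protocol's own baseline avoids the problem.** This is also correct. A window before A536-04 C1D1 cannot overlap one before A536-06 C1D1. A reader might infer that every TD analysis is affected, but the bias arises only under the SAP baseline and in the protocol's additional analysis. The SAP fallback narrows it further. A536-06 collects transfusion history from the A536-04 EOS visit as available, C1D1 may follow that visit by only 28 days, and SAP 4.1 restricts interrupted patients to A536-06 data. Early returners may therefore get the A536-04 baseline.

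**Much of the apparent response is ordinary noise.** This stands too. A reader might take the 78%, or the near-certain response in rolling windows, as regression to the mean. The comparators show otherwise: 54% occurs without selection in the first case, and almost all of the second comes from searching intervals.

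**Consequences are small.** The primary objective is safety, no hypothesis is tested, and transfusion records are listed by patient. This limits the importance. It does not remove a known upward bias from a rate with no control.

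**Conclusion.** The point holds for the fixed-window TD response rates under the SAP baseline. Any interrupted NTD patient moved to TD on the 8-week rule is measured against a baseline selected to be high. Under the stated assumptions this adds about 10 to 23 percentage points to that patient's chance of a reduction of at least 50% in weeks 13-24 with no drug effect.

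The effect on the reported rate cannot be stated, because the documents do not give the number of interrupted NTD patients; it may be small or nil. A reader might infer that such patients will all score as responders. The documents and the calculation do not support that: about half to three quarters would in weeks 13-24, many of them without any selection. Type I error and power are not involved. The correction is worth making because it is cheap and the two documents disagree on the baseline window.

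**What to change.** For analysis only, with no change to clinical handling:

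- In SAP 5.1, state the analysis status of an interrupted NTD patient with 4 or more units in the 8 weeks.
- Report TD response rates by carried-over A536-04 status. Show any interrupted NTD patient who meets only the 8-week rule separately, and give the TD rate with and without them. They remain in the ITT population.
- Reconcile the baseline-burden window in SAP 5.1 with Protocol 15.2.3, and record the outcome in SAP 5.12.6.

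Applying the 26-week rule before A536-06 C1D1 looks like an alternative but is not a cure. In the same model it admits fewer patients (six or more episodes: 1.7, 8.4 and 21.5%, against 12.7, 23.6 and 34.8%). Each is still selected on weeks that include the baseline, and about 78, 66 and 54% score a reduction of at least 50%. It can also reach into A536-04 treatment. With EOS 56 days after the last dose and C1D1 28 days later, the first A536-04 dose is as little as 84 + 56 + 28 = 168 days back, inside the 182-day window.

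The cost is SAP wording and one extra display. The TD rate may become slightly less favourable. A recently transfused patient kept as NTD may have few usable hemoglobin values, since those within 14 days after a transfusion are excluded.
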